ongoing subjects will be switched at their next scheduled study visit and subjects not yet randomized will be allocated to the selected regimen instead of being randomized. On 08 December 2016 the Sponsor made such a decision, and discontinued treatment Regimen 2. At that point, 12 subjects were included in Regimen 2, and all but 2 subjects (who had already been discontinued at that time) were transitioned to Regimen 1.

Regimen 3 – ND0612 solution will be infused subcutaneously via 2 infusion sites for 16 hrs continuously. Dosing will start upon waking. The infusion will be set to a rate of 0.75 mL/h for 16 hrs from two infusion sites in parallel, utilizing the pump system. The total infusion volume during the infusion period will be up to 12 ml (6 ml from each infusion site) which is equivalent to 720 mg LD and 90 mg CD. Subjects will remove the pump each night, after 16 hours of treatment or their bedtime, whichever comes first. Subjects in this regimen will not wear the pump overnight and will change the infusion sets and syringes, applying new ones each morning. Subjects will also take each morning oral LD/DDI (dose as needed according to investigator's assessment) at the time they wake up and start the SC treatment. Additional adjunct oral LD/DDI may be taken as needed.

Study Duration:

Planned enrollment duration: approximately 12 months

Treatment Period: 12 months of ND0612 continuous SC infusion

Optional Treatment Extension Period: Subjects will be allowed to continue with study treatment for an extension period of 24 more months (Months 12-36) during which they return for clinic visits every 3 months (Months 15, 18, 21, 24, 27, 30, 33 and 36).

Optional Long-Term Extension Period: At the end of the optional treatment extension period, subjects will be allowed to continue with study treatment for another optional long-term treatment extension period up to Month 102 during which they will return for clinic visits every 3 months up to Month 102.

Safety Follow-up Period: Safety follow up visits will be conducted for all subjects at 1, 2 and 3 months after last study treatment.

Study Population:

To be eligible for study entry subjects in Cohort 1 (previously completed the treatment period in protocol ND0612H-006 within one month prior to enrolling to ND0612H-012) must satisfy all of the following criteria:

- 1. Subject is able to, and has signed an Institutional Review Board/Ethics Committee (IRB/EC)approved informed consent form (ICF).

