11.1.1 Datasets or Populations Analyzed

The All Enrolled Set will consist of all enrolled subjects. All listings will be produced for the All Enrolled Set.

The Safety Set will consist of all subjects receiving at least 1 dose of study drug (ND0612). The Safety Set will be used for all summaries of safety and tolerability data. In addition, summaries of baseline and demographic data will also be produced for the Safety Set.

The modified Intention-to-Treat (mITT) Set will include all enrolled subjects who have valid efficacy data at baseline and at least once after the baseline. The efficacy analysis will be based on the mITT Set. The mITT Set will be used for all summaries and analyses of efficacy data.

The earlier version of this protocol included a randomization of subjects to Regimen 1 or Regimen 2. Unless stated otherwise, the subjects who received Regimen 2 and were switched to Regimen 1 during the study conduct will be included in the Regimen 1 group.

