4.1. All screened subjects

This Analysis set consists of all patients who underwent screening and will be used for summary of disposition and data listings.

4.2. Intention-to-Treat (ITT):

The ITT set will include all subjects who were randomized (before Amendment 1) or enrolled (after Amendment 1) to the study. The subjects will be grouped according to the randomized (before Amendment 1) or allocated (after Amendment 1) treatment regimen.

4.3. Safety Set:

The Safety Set will consist of all subjects (cohort 1 and cohort 2) receiving at least 1 dose of study drug (ND0612). The subjects will be grouped according to the treatment regimen actually received. The Safety Set will be used for all summaries of safety and tolerability data.

4.4. Modified Intention-to-Treat (mITT) Set:

The mITT is a subset of the ITT analysis set. The mITT Set for cohort 2 will include subjects having ON/OFF Home diary data at baseline and at least one valid post-baseline measurement. The mITT Set for in cohort 1 will include subjects having UPDRS (part III) efficacy data at baseline and at least one valid post-baseline UPDRS (part III) measurement. The subjects will be grouped according to the randomized (before Amendment 1) or allocated (after Amendment 1) treatment regimen. The mITT Set will be used for all summaries and analyses of efficacy data.

Unless stated otherwise, the subjects who received Regimen 2 and were switched to Regimen 1 during the study will be included in the Regimen 1 group. However, sensitivity analyses will be conducted by excluding the subjects who were randomized to receive Regimen 2, as specified later in this SAP.

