5. GENERAL ASPECTS FOR DATA ANALYSIS

5.1. General Methods

All data from all patients entered into the study will be included in patient data listings. The listings will be sorted by center, and patient number (and by visit, if applicable).

The data will be summarized using either descriptive statistics (number of non-missing observations, mean, median, SD, standard error of the mean (SEM), minimum and maximum) for continuous data or frequency counts and percentages for categorical data. For visit-specific data, the number of subjects with non-missing observations at the visit in question will be used as the denominator for percent calculations. Unknown, Not Done, Not Applicable and other classifications of missing data will not be considered.

The summaries will be broken down by treatment regimen (Regimen 1, Regimen 3) and by visit, as applicable. For demographic and other baseline characteristics and selected safety data, an overall column will be displayed in addition to the data broken down by the treatment regimen. Unscheduled or repeated assessments will not be included in summary tables but will be included in listings.

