7. SAFETY

7.1. General

All safety summaries will be produced for the Safety Set. In general, all safety endpoints will be summarized using either summary statistics or frequency tabulations, as applicable to the type of data.

Cohort 1 and Cohort 2 will be analyzed jointly and separately. This analysis will include the following treatment groups:

- Cohort 1, Regimen 1
- Cohort 2, Regimen 1
- Cohort 2, Regimen 3
- Cohort 2, Total
- Cohort 1+2 combined, Regimen 1
- Cohort 1+2 combined, Total

An additional safety analysis will be conducted by excluding the safety data from the patients who received Regimen 2 during the period when these patients received Regimen 2 (i.e. by excluding the data captured after the first dose of Regimen 2 until the switch to Regimen 1). This additional analysis will be done at least for extent of exposure, tolerability and selected adverse event summaries. The safety data from the optional treatment extension will be combined with the safety data of the main study and will be analyzed similarly as defined below using the Follow-up Safety Set. These analyses will be defined in more detail in the separate SAP of the optional treatment extension period.

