7.4. Tolerability and Treatment Compliance

7.4.1. Tolerability

Tolerability will be assessed based on percentage of subjects that complete the 12-month treatment period of the study and the percentage of subjects who discontinue from the 12-month treatment period due to a TEAE. Time (days) from enrolment to discontinuation will be illustrated as Kaplan-Meier curves by treatment regimen. Patients who complete the study will be right censored at the date of last dose of study treatment during the 12-month study period. Time to discontinuation will also be explored by recruitment wave 1 and 2 following corrective actions for patients' retention.

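### Ten Regimen 2 starters count in the Regimen 1 group only because they lasted to the switch, which flatters Regimen 1 completion and its retention curve

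*Protocol*

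**What the plan says.** The protocol synopsis (Treatment) counts 12 Regimen 2 subjects on 08 December 2016 and describes what became of them: "all but 2 subjects (who had already been discontinued at that time) were transitioned to Regimen 1". Protocol 8.4.5 repeats both counts.

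The grouping rule appears in protocol 11.1.1 ("the subjects who received Regimen 2 and were switched to Regimen 1 during the study conduct will be included in the Regimen 1 group") and in SAP 3.4 and 4.4 ("the subjects who received Regimen 2 and were switched to Regimen 1 during the study will be included in the Regimen 1 group"). It covers subjects who were switched and does not mention those who never were. For the Safety Set, SAP 4.3 adds: "The subjects will be grouped according to the treatment regimen actually received".

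The planned columns have no place for Regimen 2. SAP 5.1 states: "The summaries will be broken down by treatment regimen (Regimen 1, Regimen 3) and by visit, as applicable". SAP 6.2 breaks disposition down by Regimens 1 and 3 and overall. SAP 7.1 lists six safety groups: Cohort 1 Regimen 1, Cohort 2 Regimen 1, Cohort 2 Regimen 3, Cohort 2 Total, combined Regimen 1 and combined Total.

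For tolerability, SAP 7.4.1 reports the percentage completing 12 months and the percentage discontinuing because of a TEAE. It then says: "Time (days) from enrolment to discontinuation will be illustrated as Kaplan-Meier curves by treatment regimen".

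SAP 7.1 also plans an additional safety analysis, covering at least exposure, tolerability and selected adverse event summaries, which handles the Regimen 2 subjects "by excluding the data captured after the first dose of Regimen 2 until the switch to Regimen 1".

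**The concern.** Under this rule a Regimen 2 starter becomes a Regimen 1 subject only by not having discontinued before the switch. The clock still starts at enrolment. For the ten, the stretch between enrolment and switch is therefore immortal time with respect to discontinuation. They could not leave the study during it and still be in the group, yet it is displayed as Regimen 1 retention. It was also spent on a different schedule: 14 hours a day and up to 537.6 mg LD, against 24 hours and up to 720 mg. The two who did leave in that stretch have no regimen column to fall into.

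Completion and discontinuation due to a TEAE are the tolerability part of the primary endpoint (protocol 11.1.3.1, SAP 3.2.1), and the retention curves are drawn by regimen. A reader comparing Regimen 1 with Regimen 3 would see a Regimen 1 group from which some early leavers had been filtered out by construction.

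**Working it through.** The plan has no figure of its own to reproduce here. The sample size of about 210 was set without a formal calculation.

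**Inputs from the documents.** 12 subjects on Regimen 2 and 2 already discontinued, so 12 − 2 = 10 switched. The share lost before the switch is 2/12 = 16.7%. As a simple proportion, retention of the Regimen 2 starters at the switch is 10/12 = 83.3%. The ten enter the Regimen 1 curve as if it were 100%.

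**Inputs not given, so assumed.** Subjects started directly on Regimen 1, n = 20 to 60. Their 12-month completion, S = 50% to 80%. Months from enrolment to switch, t = 1 to 6. Discontinuation hazard constant and the same for the ten after the switch. If all ten switch at month t, the immortal time is 10t person-months: 10, 30 or 60 for t = 1, 3 or 6.

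**Completion.** The ten have survived to t, so their completion is c = S^((12−t)/12).

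- Planned grouping: P = (nS + 10c)/(n + 10)
- All 12 kept, the two as non-completers: (nS + 10c)/(n + 12)
- Direct Regimen 1 starters only: S

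Worked example, n = 40, S = 65%, t = 3: c = 0.65^0.75 = 0.724. P = (26 + 7.24)/50 = 66.5%. All 12 kept: 33.24/52 = 63.9%.

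| n | S | t (months) | Planned | All 12 kept | Planned minus all 12 | Planned minus direct |
|---|---|---|---|---|---|---|
| 60 | 50% | 1 | 50.4% | 49.0% | +1.4 | +0.4 |
| 60 | 80% | 1 | 80.2% | 78.0% | +2.2 | +0.2 |
| 40 | 65% | 3 | 66.5% | 63.9% | +2.6 | +1.5 |
| 20 | 50% | 6 | 56.9% | 53.3% | +3.6 | +6.9 |
| 20 | 80% | 6 | 83.1% | 78.0% | +5.2 | +3.1 |

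Differences are in percentage points, taken before rounding. Over the whole grid (n = 20, 40, 60; S = 50, 65, 80%; t = 1, 3, 6) the planned rate exceeds the all-12 rate by 1.4 to 5.2 points and the direct-only rate by 0.2 to 6.9 points. The gap to the all-12 rate equals 2P/(n + 12), which is positive whatever the assumptions.

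**Discontinuation due to a TEAE.** Let N = n + 10 be the planned Regimen 1 group, q its TEAE-discontinuation rate, and k the number of the two who stopped for a TEAE. Planned minus all-12 is q − (qN + k)/(N + 2) = (2q − k)/(N + 2). For N = 30, 50, 70 and q = 15, 25, 35%:

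- k = 0: +0.4 to +2.2 points, so the planned grouping looks worse.
- k = 1: −0.4 to −2.2 points, so it looks better (this sign needs q below 50%).
- k = 2: −1.8 to −5.3 points, so it looks better.

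The documents do not give k, so the sign cannot be settled.

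**Does the additional analysis repair it?** It removes the ten subjects' Regimen 2-period data. It states no new time origin and no late entry, so the enrolment origin of SAP 7.4.1 is the default. It does not say how the ten enter the completion percentage. The two have no switch date, so the exclusion window has no end for them, and they still have no regimen column.

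**The case against.** The strongest reply is that this touches only a descriptive breakdown. The primary objective concerns ND0612, not Regimen 1. All 12 belong to the Safety Set if dosed, and all count in the combined Total. No confirmatory regimen comparison is planned. The two are not hidden either: SAP 6.2 reports how many received any Regimen 2 and how many were switched, so they can be found by subtraction. No sentence says that they have no regimen column. That is inferred from the switch-conditional rule and the column lists, while SAP 4.3 groups by regimen received and SAP 7.4.2 gives Regimen 2 its own scheduled dose. Finally, SAP 7.1 already removes Regimen 2-period data for tolerability.

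Much of this stands, and it rules out stronger readings that a reader might infer:

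- That Regimen 1 tolerability as a whole is biased upward. This is not supported, because the TEAE component can move either way.
- That the primary result is biased, or that the two vanish from the study. This is not supported, because the main-analysis Totals hold them.
- That the ten carry time free of adverse events. They were free only of discontinuation. Their TEAEs on Regimen 2 count in Regimen 1 in the main analysis.
- That all 12 belong in Regimen 1. This conflicts with grouping by regimen received and would charge Regimen 1 with two discontinuations that happened on Regimen 2. The all-12 rate above is a yardstick, not the right Regimen 1 estimate.

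The reply does not remove the selection on surviving to the switch. A subtraction in the disposition table leaves the regimen-level rate and curve as they were, and the additional analysis lacks a late-entry rule. The efficacy sensitivity analysis (SAP 4.4, 8.1) excludes everyone randomized to Regimen 2, so membership there does not depend on the switch. Tolerability has no counterpart.

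**Conclusion.** The point holds for two outputs: the Regimen 1 completion percentage and the Regimen 1 retention curve. Both are too favourable as planned. Against keeping all 12, the upward direction for completion is certain. Its size, about 1 to 5 points, is illustrative because the number of direct Regimen 1 starters, their completion and the switch times are not given. Against direct Regimen 1 starters only, the excess of 0.2 to 6.9 points also requires similar hazards before and after the switch. On the curve, the ten swell the risk set before the switch without being able to contribute an event.

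No direction can be stated for discontinuation due to a TEAE, and the all-ND0612 Totals of the main analysis are unaffected. In an open-label study with descriptive regimen summaries, this should be corrected, but it does not threaten the main conclusion.

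**What to change.** Amend SAP 4.3, 6.2, 7.1 and 7.4.1:

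1. Show all 12 Regimen 2 starters as a separate Regimen 2-start group for disposition and tolerability, with the reasons for the two discontinuations. This also states where the two are tabulated.
2. In the additional analysis, enter the ten switchers in the Regimen 1 Kaplan-Meier curve at their switch date (left truncation), with events and exposure counted from that date.
3. In the same analysis, report the Regimen 1 completion percentages also without the ten.

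The cost is a small extra column, an entry-time variable in the Kaplan-Meier program and a few sentences of SAP text. No new data are needed beyond the switch dates. Regimen 1 completion may become slightly less favourable.

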5 LIST OF ABBREVIATIONS AND DEFINITION OF TERMS

LIST OF ABBREVIATIONS

ADL	Activities of Daily Living
AE	Adverse Event
AESI	Adverse Event of Special Interest
ALT	Alanine Aminotransferase
AST	Aspartate Aminotransferase
AUC	Area under the plasma concentration vs. time curve
BP	Blood Pressure
BUN	Blood Urea Nitrogen
C-SSRS	Columbia - Suicide Severity Rating Scale
CD	Carbidopa
CGI	Clinical Global Impression
CRO	Contract Research Organization
DDI	Dopa Decarboxylase Inhibitor
DMC	Data Monitoring Committee
EC	Ethics Committee
ECG	Electrocardiogram
eCRF	Electronic Case Report Form
EDC	Electronic Data Capture
EQ-5D-5L	EuroQol Group 5-dimensions, 5-level Quality of Life questionnaire
ESS	Epworth Sleepiness Scale
FDA	Food And Drug Administration
Gamma GT	Gamma Glutamyltranspeptidase
GCP	Good Clinical Practice
GDPR	General Data Protection Regulation
hr(s)	Hour(s)
HBsAg	Hepatitis B Surface Antigen
HCV	Hepatitis C Virus Antibody
HIV	Human Immunodeficiency Virus
ICF	Informed Consent Form
ICH	The International Conference on Harmonisation of Technical
	Requirements for Registration of Pharmaceuticals for Human Use
IR	Immediate Release
IRB	Institutional Review Board
IWRS	Interactive Web Response System
LD	Levodopa
MedDRA	Medical Dictionary For Regulatory Activities
mITT	Modified Intention-to-Treat
mL/µL	Milliliter/Microliter
MMSE	Mini Mental State Examination
mmHg	Millimeter(s) of Mercury
MMRM	Mixed Model for Repeated Measures
n	Number of subjects with an observation
N	Number of subjects in the dataset or population
PDO 20	Parkinson's Disease
PDQ-39	59-Item Parkinson's Disease Quality of Life Questionnaire
PDSS PV	Parkinson's Disease Sleep Scale
РК	Pharmacokinetics

ND0612H-012

Neuro**Derm**

Version 10.0

PT	Preferred Term
QUIP-RS	Questionnaire for Impulsive-Compulsive Disorders in Parkinson's
	Disease-Rating Scale
QoL	Quality of Life
SAE	Serious Adverse Event
SGI-I	Subject Global Impression of Improvement
SAP	Statistical Analysis Plan
SC	Subcutaneous(ly)
SD	Standard Deviation
SOC	System Organ Class
SUSAR	Suspected Unexpected Serious Adverse Reaction
t _{1/2}	Half-Life
TEAE	Treatment emergent Adverse Event
ULN	Upper Limit of Normal
UPDRS	Unified Parkinson Disease Rating Scale
USA	United States of America
VAS	Visual Analogue Scale
WHO	World Health Organization

DEFINITION OF TERMS

"OFF" state	Phase with no response to medication and significant motor symptoms
"ON" state	Phase with good response to medication and few symptoms

6 INTRODUCTION

6.1 Background

Parkinson's disease (PD) is a neurodegenerative movement disorder characterized by tremor, bradykinesia, muscular rigidity, and gait impairment as a result of marked dopamine deficiency in the basal ganglia of the brain due to the loss of dopaminergic neurons [1, 2]. Dopamine itself does not cross the blood-brain barrier, but its metabolic precursor, levodopa (LD), can permeate into striatal tissue and has, therefore, been an important drug in the treatment of the disease. For the past 40 years, LD (or L-Dopa) has remained the most effective therapy for the treatment of PD.

Under normal conditions, there is a low but continuous release of dopamine in the brain with superimposed bursts of increased release. However, LD has a short half-life $(t_{1/2})$ in plasma that, even under the best common current standard of care, results in pulsatile dopaminergic stimulation which differs from the physiological pattern of neurotransmitter secretion. The pulsatile manner in which LD or other short-acting dopaminergic agents stimulate striatal dopamine receptors is a key in the priming of the basal ganglia for induction of motor complications [3, 4, 5, 6, 7], i.e. motor fluctuations and dyskinesia that can represent a source of significant disability for the subjects, resulting in reduced overall effectiveness after 2 or 3 years of treatment. Carbidopa (CD) was developed to attenuate the adverse effects of LD therapy, such as nausea and vomiting as well as neurological deficits [8]. Proposed mechanisms include gastrointestinal dopa decarboxylase inhibition (DDI) to increase bioavailability. systemic DDI to decrease the plasma clearance, and brain capillary DDI to promote entry of L-dopa into brain tissue. Attempts are being made to provide more sustained dopamine concentrations in the central nervous system, known as continuous dopaminergic stimulation, by using novel LD preparations [2, 5, 9]. The current available long acting oral LD therapies failed to reduce the risk of motor complications in controlled trials [10, 11, 12]. In contrast, long lasting and dramatic reductions in motor complications associated with reduced dyskinesias and "OFF" periods (phases with no response to medication and significant motor symptoms) have been observed in PD subjects when treated with continuous infusion of LD (intravenous or intraduodenal) or dopamine agonists [1, 6, 8, 11, 13]. Unfortunately, the infusion approaches to date have inherent limitations in that they are neither convenient nor practical treatment options and dopamine agonists fail to reach the efficacy of LD and bear major adverse effects [14].

Levodopa and CD have been used extensively in humans by the oral route. NeuroDerm, Ltd. (NeuroDerm) is developing combination products comprising an LD/CD solution for continuous subcutaneous (SC) administration via different infusion pump systems for the treatment of idiopathic PD. The LD/CD solution contains 60 mg/mL LD and 7.5 mg/mL of CD.

ND0612 is being developed for patients with LD-responsive PD who do not have satisfactory control of debilitating motor fluctuations and hyper-/dyskinesia despite optimized treatment with commercially available PD products.

Neuro Derm			28 December 202
ND0612H-012	Vers	ion 10.0	Page 24 of 23
		-	
			2

Neuro Derm		28 December 2020
ND0612H-012	Version 10.0	Page 32 of 232
· .		
		5
· •		
		22

Eight completed clinical studies have evaluated a wide range of ND0612 exposures in healthy volunteers and patients with PD. LD and CD PK have been extensively evaluated, and safety and tolerability of infusions (with daily change of infusion sites) has been demonstrated with regard to both ND0612 study drug and the SC delivery system.

6.5 Study Plan

This Phase IIb open-label safety study is conducted in approximately 210 subjects who belong to 1 of 2 cohorts:

Cohort 1 includes subjects with advanced PD who are currently being treated (within the past month) with ND0612 in study ND0612H-006. They were planned to remain on the treatment regimen that they received in the ND0612H-006 study. From 08 December 2016 onwards, all subjects who were treated with Regimen 2 were to be switched to Regimen 1 and newly enrolled subjects were allocated to Regimen 1 (see Section 8.4.5 for details).

Cohort 2 includes subjects with advanced PD who completed any ND0612 study more than one month ago, or were not previously enrolled in any of the ND0612 protocols ("ND0612 naive subjects"). Cohort 2 subjects were randomized (1:1 ratio) to treatment regimens 1 or 2 (described below and in Section 8.1.1) up to 08 December 2016. After this date, all Cohort 2 subjects were allocated to Regimen 1 instead of being randomized (see Section 8.4.5 for details). After the implementation of Protocol amendment 2, all subjects enrolled in Cohort 2 receive Regimen 3. Total enrolment will be approximately 210 subjects.

The study will primarily investigate the safety (with a focus on local safety) and tolerability of continuous SC infusion of 3 dosing regimens of ND0612; efficacy will be assessed in an exploratory manner. Regimen 1 will employ continuous infusion for 24 hrs using a low infusion rate at night and a higher rate at daytime, resulting in a daily dose of 720 mg LD and 90 mg CD and additional oral LD/DDI as needed. Regimen 2 will employ infusion for 14 hrs only during daytime (at an infusion rate of 0.64 mL/hr; daily dose: 537.6 mg LD and 67.2 mg CD) with supplemental administration of oral immediate release (IR) LD/CD (150/15 mg) in the mornings. Regimen 3 will employ infusion for 16 hrs only during daytime (at an infusion rate of 0.75 mL/hr; daily dose: 720 mg LD and 90 mg CD) with supplemental administration of oral immediate and 90 mg CD) with supplemental administration of oral LD/DDI in the mornings and additional oral LD/DDI as needed.

For Cohort 2, subjects and study partners will receive training on administration of the SC infusions during the screening period by the Home Nursing Service. During the Baseline visit (Day 1) the site staff will supervise the administration of the infusion.

For both cohorts, if required, subjects and their study partners will be trained and assisted at their homes during the first week of treatment by the Home Nursing Service on the correct administration technique. One mandatory home visit will be performed during the first week, preferably on Day 3. Throughout the 12-month treatment period the Home Nursing Service will visit the subjects at their homes on a monthly basis.

For both cohorts, during the treatment period (up to Month 102), a helpline will be available for subjects/study partners to call at any time should they encounter any difficulties with the pump system.

The planned treatment duration for all regimens is 12 months with in-clinic visits at Week 1, Month 1, Month 2, Month 3, Month 4, Month 6, Month 9 and Month 12.

Subjects will be allowed to continue with study treatment for an optional treatment extension period of 24 more months in which clinic visits will be performed every 3 months to assess subject safety. Subjects will be offered another optional long-term treatment extension period up to Month 102. During this long-term extension period, clinic visits will continue to be performed every 3 months to assess subject long-term safety.

Safety follow-up visits will be performed 1, 2 and 3 months after the last SC administration of the study drug.

This will be the third study to assess the administration of the ND0612 solution using different dosing regimens in a home setting, with the focus of the current study being on the safety of long-term home administration. Additionally, the study will explore the need for dose adjustments e.g., up and down titrations of the study drug and/or a need for additional oral anti-PD treatment.

